#### **If Year of AE start date is missing:**

If the year of AE start is missing or AE start date is completely missing, then query site and leave as missing.

For missing and partial adverse event end dates, imputation will be performed as follows:

If only the day of the month is missing, the last day of the month will be used to replace the missing day. If the day and month are missing or a date is completely missing, it will be considered as missing.

Imputation rules for missing or partial medication start/stop dates are defined below:

#### **If only Day of CM start date is missing:**

If the CM start year and month are the same as that for the first dose date, then:

- If the full (or partial) CM end date is NOT before the first dose date or CM end date is missing, then impute the CM start day as the day of first dose date;
- Otherwise, impute the CM start day as 1.

#### **If Day and Month of CM start date are missing:**

**Final Analysis**  
**Statistical Analysis Plan (SAP)**

If CM start year = first dose year, then:

- If the full (or partial) CM end date is NOT before the first dose date or CM end date is missing, then impute the CM start month and day as the month and day of first dose date
- Otherwise, impute the CM start month as January and the day as 1.

**If Year of CM start date is missing:**

- If the year of CM start is missing or CM start date is completely missing, then query site and leave as missing.

## **8 STATISTICAL METHODS**

### **8.1 General statistical conventions**

All statistical procedures will be completed using SAS version 9.4 or higher.

Unless otherwise stated, all statistical testing will be two-sided and will be performed using a significance (alpha) level of 0.05. Two-sided 95 % confidence intervals (CI) will be provided when relevant. Any p-value below 0.05 will be displayed to 4 decimal places.

Any p-value less than 0.0001 will be displayed as <0.0001. Any p-value between 0.05 (inclusive) and 0.10 will be displayed to 3 decimal places and any p-value greater than 0.10 will be displayed to two decimal places. Any p-value greater than 0.9999 will be displayed as >0.99.

All quantitative endpoints will be summarized using an 8-number summary (n, mean, standard deviation, median, 25th percentile, 75th percentile, minimum and maximum values). The mean and median and the percentiles will be rounded to one decimal place beyond the precision of the values being summarized, the standard deviation will be rounded to 2 additional decimal places beyond this precision and the minimum and maximum values will be displayed in the same precision. All qualitative endpoints will be summarized by the number of subjects meeting the endpoint and the percentage of subjects out of the appropriate population. The denominator will be displayed when needed and the percentage will be rounded to one decimal place

All subject data, including those derived, will be presented in individual subject data listings. Unless otherwise stated, unscheduled visit results will be included in date/time chronological order, within subject listings only. All listings will be sorted by investigational site, patient number, date/time, and visit. The treatment group as well as patient's sex and age will be stated on each listing. Unless otherwise stated, data listings will be based on all subjects randomized.

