### **8.3.5. Assessment of Pruritus**

Pruritus will be monitored in this study at the times indicated in the [Schedule of Assessments](#). As listed below, two separate scales may be used to assess pruritus in subjects:

- First, an itch visual analog scale (VAS) will be used to record the intensity of the event ([Furie et al., 2013](#)). Site personnel should instruct the subject to draw a line on the scale corresponding to the maximum intensity of itch within the last two weeks.
- If VAS score is greater than zero (i.e. itch), a multidimensional 5D-itch scale developed by Elman ([Elman et al., 2010](#)) will be used to assess five different dimensions of pruritus within the last two weeks. The five dimensions assessed are duration, degree, direction, disability, and distribution.
- The scales should be administered as indicated in the study binder.

The scales will be completed by the subject in the clinic during the visit for the in-clinic visits as indicated in the [Schedule of Assessments](#). For the Day 7 phone contact, the subject will be given a copy of the scales on Day 1 to take home so that he/she can record pruritus on Day 7 ( $\pm 1$  day), preferably immediately preceding or during the phone contact with the site.

In addition, **if a subject experiences pruritus** between clinic visits the subject should contact the site as soon as possible:

- to discuss the event,
- to obtain guidance on how to manage the side effect(s),
- and to get specific instructions on how to complete the VAS, 5D-itch and additional evaluations through resolution of the event.

Additional details relative to management of subjects who experience pruritus are included in a separate study binder.

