**Table 6: Retest Frequency Recommendations**

Trends Observed for Repeat Liver Function Test	Frequency for Repeat Tests
First 3 repeat tests (including test to confirm initial alert test result)	Every 48 – 72 hrs
Increasing tendency of test result	Every 48 – 72 hrs
Stabilization of test result	Once weekly
Decreasing tendency	Once weekly – every 2 weeks

Depending on the course of the liver transaminase retest results, on a case-by-case basis, a gastroenterology or hepatology consultation or additional liver biopsy for any subject with persistent evidence of liver injury might be indicated.

If a subject lives in a remote area, they can be tested locally with the results promptly communicated to the PI site. However, testing via central lab is the preferred option.

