### **8.7.2 Lab Based Stopping Rules**

Summaries will be provided using counts and percentages for subjects who meet the stopping rules as described below:

- If ALT or AST increases to  $>5\times$  Reference baseline (and is at least  $> 5x$  ULN)
- If ALT or AST increases to  $>2\times$  Reference baseline (and is at least  $> 3x$  ULN) AND the increase is accompanied by
  - a concomitant total bilirubin increase to  $>2\times$  Reference baseline (and at least  $> 2x$  ULN) OR
  - the INR is concomitantly  $> 1.5$
- If ALT or AST increases to  $>2\times$  Reference baseline (and is at least  $> 3x$  ULN) AND
  - elevations of ALT/AST are accompanied by signs or symptoms of right upper quadrant abdominal pain, anorexia, nausea, vomiting, fever, eosinophilia ( $>$  upper limit of normal of absolute eosinophilia count), and/or rash.

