#### **8.7.2.1 Close Monitoring for Drug Discontinuation due to Elevated ALT/AST**

The following close observation guidelines applies to subjects that repeat assessments show persistent elevations of transaminases, but who do not meet drug discontinuation criteria, and for subjects who discontinue study drug due to ALT/AST elevations.

Close monitoring activities will be initiated:

- If ALT or AST increases  $> 2x$  Reference baseline (and is at least  $> 3x$  ULN) OR
- If ALT or AST increases  $> 8x$  ULN (whichever comes first)

Details related close monitoring is available in protocol section 10.2.

A listing will be used to track and evaluate subjects that are part of the close observation guidelines.

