## Final Analysis

### Statistical Analysis Plan (SAP)

will be included in these summaries. Baseline is defined as the last value collected prior to first dose of study drug.

The number and percentage of subjects with treatment-emergent laboratory abnormalities until the last dose of study drug will be summarized by treatment group. In addition, shift from baseline tables will be generated by visit and treatment group.

For categorical tests: Treatment-emergent abnormal is defined as a change from normal at baseline to abnormal at any post-baseline visit

For continuous tests:

- Treatment-emergent high is defined as a change from a result less than or equal to the high limit at baseline to a value greater than the high limit at any time post-baseline.

Results will be reported according to any value greater than the high limit, any value greater than 2x ULN and 3x ULN

- Treatment-emergent low is defined as a change from a result greater than or equal to the low limit at baseline to a value less than the low limit at any time post-baseline
- Results will be reported according to any value less than the lower limit, any value less than 2x LLN and 3x LLN.

All summary tables will include the abnormalities that occur during the treatment-free follow-up after the date of last dose. The denominator for these will include any subject who entered into the 4 week treatment-free follow-up phase.

All laboratory data will be included in the data listings and all test values outside the normal range will be flagged as low or high.

Separate listings will be provided for: Pregnancy test, FSH, HIV, HCV, and HBV along with biomarkers for NASH (Cytokeratin (CK)18, GLP-1 (glucagon-like peptide-1)).

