## Final Analysis Statistical Analysis Plan (SAP)

### Appendix C – Analysis Visit Windows

For the purpose of conducting analyses, the visit windows noted below will be utilized for binning study visits. In the event that multiple visits fall within the same window, the scheduled visit will take precedence. If the scheduled visit was not attended, the closest visit to the target within the window will be utilized. If multiple visits are equidistant from the target date, the later of the two visits will be used.

Nominal Visit	Visit Window Lower Bound	Visit Target (Days)	Visit Window Upper Bound
Screening	N/A	N/A	-1
Day 1	1	1	1
Day 7	4	7	10
Week 2	11	14	20
Week 4	21	28	41
Week 8	42	56	69
Week 12	70	84	97
Week 16	98	112	125
Week 20	126	140	153
Week 24	154	168	181
Week 28	182	196	209
Week 32	210	224	237
Week 36	238	252	265
Week 40	266	280	293
Week 44	294	308	321
Week 48	322	336	363
Week 56	364	392	419
Week 64	420	448	475
Week 72	476	504	517
Week 76	518	532	N/A

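### Under the SAP 8.1 default, a liver stopping threshold first crossed at a protocol-required retest can drop out of the SAP 8.7.2 stopping-rule counts

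*SAP*

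**What the plan says.** SAP 8.1 sets the default for unscheduled data: "Unless otherwise stated, unscheduled visit results will be included in date/time chronological order, within subject listings only". It is a default, since it yields wherever the SAP states otherwise.

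SAP 8.7.2 then plans the liver table: "Summaries will be provided using counts and percentages for subjects who meet the stopping rules as described below". It repeats the ALT/AST, bilirubin, INR and symptom criteria of Protocol 10.1 and does not say which results feed the count. Subjects under close monitoring get no table: "A listing will be used to track and evaluate subjects that are part of the close observation guidelines" (SAP 8.7.2.1).

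SAP 8.7.3 defines a treatment-emergent high as a move from at or below the limit at baseline "to a value greater than the high limit at any time post-baseline", and adds: "Results will be reported according to any value greater than the high limit, any value greater than 2x ULN and 3x ULN".

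Appendix C, on binning visits, says: "In the event that multiple visits fall within the same window, the scheduled visit will take precedence". If the scheduled visit was missed, the closest visit in the window is used.

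In the protocol, Section 10.1 stops drug on a single qualifying result, with no repeat needed. Section 10.2 starts close monitoring at a lower level and asks for retests within 48 to 72 hours. Table 6 keeps that spacing for the first three repeats, and local testing is allowed for subjects in remote areas.

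**The concern.** The alert level lies below the main stopping level, and the protocol fills the gap with tests outside the visit schedule. For a subject who is in alert but not yet at a stopping threshold, the value that decides the matter will often be a retest. That applies to ALT or AST reaching 5 times Reference Baseline, and equally to a bilirubin or INR result that completes a combined criterion.

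A programmer who follows SAP 8.1 and finds no exception in 8.7.2 would leave those results out of the table. The omission can only lower a count, and it lowers it most in the arm with the most alerts that go on to cross.

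The table is still due. SAP Section 9 lists the analyses cancelled after termination, and 8.7 is not among them. With the histology analyses gone, safety is a main remaining output.

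**Working it through.** **No plan figure to reproduce.** The SAP gives no expected count, so the check is a reading of the text plus a bound under stated assumptions.

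**1. Do retests fall outside the by-visit data?** I placed three retests, 2 or 3 days apart, after each scheduled visit (early, on time or late within its tolerance) into the Appendix C windows.
- From Week 4 onward, all three fall in that visit's own window. At Week 12, the latest case is 84 + 3 + 9 = day 96, against an upper bound of 97. The attended scheduled visit then takes precedence.
- After an on-time Week 2 visit with 3-day spacing, the third retest is 14 + 9 = day 23. This is in the Week 4 window (from day 21) and is used only if Week 4 was missed.

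**2. Thresholds.** Let RB be Reference Baseline.
- Alert (Protocol 10.2): above 2 × RB and above 3 × ULN, or above 8 × ULN.
- First stopping rule (Protocol 10.1): above 5 × RB and above 5 × ULN.

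Illustration with assumed values ULN 40 and RB 60:
- The alert is at 120, since 2 × 60 = 3 × 40 = 120. The stop is at 300, since 5 × 60 = 300 exceeds 5 × 40 = 200.
- A scheduled Week 8 ALT of 190 is an alert only.
- With a 7-day doubling time, the day-3 retest is 190 × 2^(3/7) ≈ 256 (4.3 × RB), which is not a stop.
- The day-6 retest is 190 × 2^(6/7) ≈ 344 (5.7 × RB), which is a stop. Day 56 + 6 = 62 is inside the Week 8 window (42 to 69).

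Under the 8.1 default this subject is counted in 8.7.2 only if a scheduled or end-of-treatment sample is also above 300.

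**3. Upper bound on the share affected.** Assume an exponential rise, visits every 28 days, and alert crossings spread evenly between visits. A scheduled value lands between alert and stop with probability log2(stop/alert) × doubling time / 28.

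| Reference Baseline | stop/alert | doublings | 7 days | 14 days | 21 days |
|---|---|---|---|---|---|
| at or below ULN | 5/3 | 0.737 | 18% | 37% | 55% |
| 1.5 to 4 × ULN | 5/2 | 1.322 | 33% | 66% | 99% |

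Between 1 and 1.5 × ULN, the ratio runs from 5/3 to 5/2. Above 4 × ULN the 8 × ULN alert comes first (2 × 4 = 8) and the gap widens further; that case is not tabulated. These are upper bounds because a later scheduled or end-of-treatment value may still exceed the threshold.

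**4. Does SAP 8.7.3 replace the count?** Its wording can fairly be read as admitting unscheduled results, but:
- its highest cut is 3 × ULN, below the 5 × ULN in the first stopping rule;
- it does not use Reference Baseline;
- it has no combined bilirubin, INR or symptom criterion;
- it covers only subjects at or below the limit at baseline, while entry allows ALT and AST up to just under 5 × ULN.

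**The case against.** The best reply is that 8.7.2 counts subjects who meet a rule. That is a subject-level event with no by-visit wording, so using every result is at least as natural a reading. Appendix C governs binning and does not define this count. Both points are fair, and they make the omission a literal reading and not a certainty. They do not remove it: 8.1 asks for an exception to be stated, and 8.7.2 states none.

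Other parts of the reply stand and limit the point:
- A crossing at a scheduled visit is counted, because no repeat is required. Early stoppers also have an end-of-treatment visit with safety labs within a week of the last dose.
- Liver-related stops reported as adverse events appear among TEAEs leading to discontinuation, and all stops appear in disposition. Neither table shows which liver rule was met.
- The rise kinetics are assumed. Nothing in the documents supports one doubling time over another.

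A reader might infer that unscheduled results never reach any safety table. The qualifier in 8.1, the wording of 8.7.3 and the missed-visit fallback in Appendix C all say otherwise. Nor is harm shown for vital signs (8.7.4) or ECGs (8.7.6).

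A reader might also infer an error in the pruritus analysis, because Protocol 8.3.5 has subjects with itch between visits contact the site "to get specific instructions on how to complete the VAS, 5D-itch and additional evaluations through resolution of the event". Two-week recall at scheduled visits covers 4 + 11 × 2 + 3 × 2 = 32 of 72 weeks (44%). But that is calendar coverage, not itch missed. Scores prompted by symptoms would distort by-visit means and are rightly kept out of them. Pruritus is also tabulated as a TEAE whatever its timing. How often between-visit scores are taken is left to site instructions and the study binder, which are not available here.

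**Conclusion.** The concern holds for the stopping-rule counts in SAP 8.7.2. Followed literally, the SAP may omit a subject whose ALT or AST, or accompanying bilirubin or INR, first crosses a stopping threshold at a retest the protocol requires. No other planned table supplies that count.

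The true undercount is unknown. For the 5-fold rule, the bound runs from 18% (Reference Baseline at or below ULN, 7-day doubling) to 99% (1.5 to 4 × ULN, 21-day doubling). Those figures describe the assumptions more than the trial. They apply to 4-weekly visits, and doubling the spacing to 8 weeks halves them. The combined bilirubin, INR and symptom rules are not quantified.

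For itch, the documents support at most a useful extra summary.

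**What to change.** - In SAP 8.1 and Appendix C, confine the listings-only rule and the precedence of scheduled visits to by-visit summaries.
- In SAP 8.7.2 and 8.7.3, state that subject-level threshold and abnormality counts use every post-baseline result, scheduled or unscheduled, central or local.
- Show the number of unscheduled tests per arm beside these counts.

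The cost is a few sentences of SAP text and one added row or small table, using liver results the protocol already calls for. The small downside is that more tests give more chances to cross a threshold, which is why the test numbers should be shown.

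Optional and secondary: a descriptive worst post-baseline VAS and 5D-itch score by arm, including any between-visit scores collected under Protocol 8.3.5. The by-visit and MMRM pruritus analyses should stay as they are.

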## **8.2 Subject disposition**

All subjects who provided informed consent will be included in a summary of subject accountability. The number and percentage of subjects screened, randomized, randomized and treated, randomized and not treated, as well as the number and percentage of subjects in each analysis population (safety, ITT, PP, and PK) will be summarized. The denominator for the calculation of percentages will be from the number of subjects randomized.

The following categories will also be summarized for subject disposition by treatment group and overall:

- Completed study drug per protocol
- Discontinued study drug early and the primary reason for study drug discontinuation
- Completed the study (i.e., completed safety follow-up at Week 76)
- Discontinued from the study early and the main reason for discontinuation

## **8.3 Protocol deviations**

All protocol deviations identified will be summarized by treatment group and overall, all protocol deviations will be listed.

Summaries of major protocol deviations (counts & percentages) will be provided by deviation categories & subcategories for all subjects that were randomized.

## **8.4 Demographics and baseline characteristics**

No statistical testing will be performed for the comparison between treatment groups on demographics and baseline characteristics.

A by-subject listing will be provided.

### **8.4.1 Demographics**

The following subject demographics will be summarized in the table by randomized treatment group for all subjects in the safety population: age, gender, ethnicity, race, height, weight and BMI at baseline.

### **8.4.2 Baseline and disease characteristics**

T2DM status, use of Vitamin E and/or pioglitazone, fibrosis score, NAS score, individual NAS components (steatosis, lobular inflammation, ballooning) at baseline will be summarized for the safety population. The categorical baseline characteristics such as ECG and selected lab parameters (i.e., ALT, AST, Total Bilirubin, LDL, HDL, C4, and FGF) will be summarized using frequency counts for the safety population.

### **8.4.3 Medical history**

A summary of medical and surgical history will be presented by system organ class (SOC) and preferred term (PT) using Medical Dictionary for Regulatory Affairs® (MedDRA) Version 23.0 or higher for the safety population.

A by-subject listing will be provided.

#### **8.4.4 Prior and concomitant medications/ procedures**

Medications used in this study will be coded by using the World Health Organization Drug Dictionary Enhanced (WHODDE) version “WHO Drug Global B3 Mar2021”.

**Prior medications/ procedures:** are defined as those medications/ procedures with a start date prior to the first dose of study drug.

**Concomitant medications/ procedures:** are defined as those medications/ procedures with a start date on or after the first dose of study drug until the last dose. A medication/ procedure which started prior to dosing and continued after dosing will also be considered as concomitant medication/ procedure.

Prior and Concomitant medications will be summarized descriptively using frequency tables by anatomical therapeutic chemical (ATC) class and preferred name by treatment group on the safety population. Concomitant diabetes medications will be summarized using the same format.

Prior and Concomitant procedures will be summarized descriptively using frequency tables by treatment group on the safety population.

A by-subject listing will be provided for prior and concomitant medications.

Details for imputing missing or partial start and/or stop dates of medication are described in [Section 7.2.2](#).

### **8.5 Extent of exposure**

#### **8.5.1 Treatment duration**

Duration of study drug (in days) will be calculated as: last dose date – first dose date + 1 day, regardless of study drug interruption.

Study drug exposure will be summarised by treatment group on the safety population using descriptive statistics.

#### **8.5.2 Treatment compliance**

Study drug compliance will be based on the amount of drug taken. The derivation for the treatment compliance is provided in [Table 2](#). The maximum percentage of drug taken will be 100%.

Study drug compliance will be summarized by treatment group using 8-number summary. They will also be summarized in categories “<80%, 80% - <90%, 90% - <100% and “≥100% compliant” using frequency tables.

Study drug compliance summaries will be based on the safety population.

A by-subject listing of randomization schedule and study drug dispensed with LOT number will be provided.

## **8.6 Efficacy analyses**

This section addresses separately the analyses to be conducted on the primary, secondary, and exploratory efficacy variables. All the efficacy analyses will be performed using ITT population as primary analysis.

### **8.6.1 Analysis methods**

#### **Logistic Regression Model for proportion of responders**

Endpoints looking at a proportion of responders will be analyzed by logistic regression. The SAS procedure PROC GENMOD will be used. The preferred model will include the fixed categorical effects of treatment group, diabetes status and use of Vitamin E and/or pioglitazone. Baseline NAS score will be included as covariate. The model will be used to derive odds ratio, confidence interval and p value. A sample of SAS code for logistic regression is provided in [Appendix A](#).

Fisher exact test will be used to test the treatment difference in case the model does not converge. A sample of SAS code for Fisher exact test is provided in [Appendix A](#).

